#### CONFIDENTIAL AND PROPRIETARY

This document contains information that is confidential and proprietary to Smith & Nephew PLC and Smith & Nephew, Inc. and is intended for use only by Smith+Nephew and its manufacturer. It shall not be reproduced or copied in whole or in part, nor shall the contents be disclosed by any means without prior written permission from Smith+Nephew, nor shall anyone make any use of it that is contrary to the expressed or implied wishes of Smith+Nephew.  
TMP-CD-05-01 Clinical Protocol - Device - Revision D; SOP-CD-05 Clinical Protocol

Clinical Protocol	Study Number: CORI.2019.06
A Prospective, Multi-center, Randomized Controlled Study to Evaluate the Safety and Effectiveness of REAL INTELLIGENCE™ CORI™ in unicondylar knee arthroplasty (UKA) Procedure	Version: 4.0-Master, 07 Sep 2022
	Page: 59 of 167

network-based randomization system. A randomization number is allocated only when subjects have signed the Informed Consent Form and satisfy all study eligibility criteria.

### **8.5.3 Subject Attrition**

Subject attrition for the sample size has been accounted for in the sample size estimation.

### **8.5.4 Pre-specification of Statistical Analysis**

The primary outcome measure has been pre-specified as well as the type of statistical analysis to be performed in order to evaluate this outcome. The details of all analyses to be performed will further be pre-specified in the Statistical Analysis Plan (SAP) so as to minimize any threats to external validity and yield clinically relevant estimates of effects and precision.

## **9 STUDY PROCEDURES**

### **9.1 VISITS AND EXAMINATIONS**

#### **9.1.1 Summary**

For a summary of the required procedures by visit, refer to the Study Schematic Table 9.1.1-9-1 Study Procedures by Visit.

**Table 9.1.1-9-1 Study Procedures by Visit**

Schedule of events	Pre-Operative Data -90 to 0 days	Operative Data & Discharge Day 1 (+ up to 9 days)	6 weeks 42 ± 14 days	6 months 185 ± 14 days	12 months 365 ± 30 days
Informed Consent	x				
Demographics/ Medical History	x				
Inclusion/Exclusion	x				
Preoperative Examinations (eg. ECG, Blood Routine Examination, Biochemical Examination, Coagulation Examination) 	x				
Pregnancy Test 	x				
Concomitant Medication	x				
Concomitant Medication Update		x	x	x	x
Operative Data Collection		x			
CORI Case Report (System time & cutting time)		x			
Discharge Data Collection		x			
Leg alignment Long leg X-ray AP 	x	(x) 	x		(x) 
Standard Lateral X-ray		(x) 	x		x
Standard A/P X-ray					x

## CONFIDENTIAL AND PROPRIETARY

This document contains information that is confidential and proprietary to Smith & Nephew PLC and Smith & Nephew, Inc. and is intended for use only by Smith+Nephew and its manufacturer. It shall not be reproduced or copied in whole or in part, nor shall the contents be disclosed by any means without prior written permission from Smith+Nephew, nor shall anyone make any use of it that is contrary to the expressed or implied wishes of Smith+Nephew.

Clinical Protocol			Study Number: CORI.2019.06		
A Prospective, Multi-center, Randomized Controlled Study to Evaluate the Safety and Effectiveness of REAL INTELLIGENCE™ CORI™ in unicondylar knee arthroplasty (UKA) Procedure			Version: 4.0-Master, 07 Sep 2022		
			Page: 61 of 167		

KSS	x		x	x	x
OKS	x		x	x	x
FJS-12			x	x	x
EQ-5D-5L	x		x	x	x
Safety Assessment		x	x	x	x
End of Study/Exit			(x) 	(x) 	x

 Only applicable at sites in China

 Only Applicable at site in China

 Pre-operative long leg X-rays (A/P) collected 6-months prior to the date of surgery is admissible

 Post-operative standing weight bearing long leg X-rays (A/P) and standard lateral X-rays may be taken at discharge.

 Only if standing weight bearing long leg A/P X-ray is taken as a standard of care at 12 months.

 Exit form to be completed at the point of withdrawal if the study is not completed.

### 9.1.2 Screening/Pre-operative Visit

1. Obtain written informed consent from the subject as detailed in Section 7.5.  
----- ***Do not proceed until the consent has been obtained*** -----
2. Obtain demographic information and medical history, including information on all concomitant medications/therapies.
3. Screen the subject for protocol inclusion/exclusion criteria.
4. The eCRF will assign the subject a study number. The subject identification log shall be completed accordingly.
5. Instruct the subject on treatment procedures.
6. Collect radiographic images of the affected knee for evaluation of leg alignment (Standing weight bearing A/P long leg X-ray).
7. Collect the 2011 KSS score objective measures (joint alignment, instability, motions & symptoms).
8. Have the subject complete the 2011 KSS score subject questions.
9. Have the subject complete the OKS patient-reported outcome measure.
10. Have the subject complete the EQ-5D-5L patient-reported outcome measure.
11. The subject will be randomized to treatment group (CORI or Manual conventional instrumentation).
12. Subjects will be instructed to return for the Operation Visit on a scheduled date.

### 9.1.3 Operation Visit & Discharge (Day 1+up to 9 days)

1. Prior to surgery, check if there is any change in eligibility of the subject since the pre-operative visit. If the subject is no longer eligible, document as screening failure.

#### CONFIDENTIAL AND PROPRIETARY

This document contains information that is confidential and proprietary to Smith & Nephew PLC and Smith & Nephew, Inc. and is intended for use only by Smith+Nephew and its manufacturer. It shall not be reproduced or copied in whole or in part, nor shall the contents be disclosed by any means without prior written permission from Smith+Nephew, nor shall anyone make any use of it that is contrary to the expressed or implied wishes of Smith+Nephew.

TMP-CD-05-01 Clinical Protocol - Device - Revision D; SOP-CD-05 Clinical Protocol

Clinical Protocol	Study Number: CORI.2019.06
A Prospective, Multi-center, Randomized Controlled Study to Evaluate the Safety and Effectiveness of REAL INTELLIGENCE™ CORI™ in unicondylar knee arthroplasty (UKA) Procedure	Version: 4.0-Master, 07 Sep 2022
	Page: 63 of 167

2. Query subject regarding any changes in general health and the use of concomitant medications/therapies.
3. Collect data on the surgical plan: Target Leg alignment.
4. Perform surgery and collect intra-operative data on the appropriate eCRF. This includes but is not limited to the following information:
  - Knee Implant Data
  - Surgical data (e.g. duration, blood loss, surgical approach)
  - Collect pre- (with the trial implant in place) and post cementation alignment with the use of CORI.
  - Collect the Subject's CORI Case Report, generated CORI Software (System time, cutting time) for CORI group.
5. Complete discharge eCRF.
6. If any adverse device effects or device deficiencies are observed or reported, they must be recorded as instructed in Section 12 - Adverse Events and Device Deficiencies.
7. Instruct the subject on proper postoperative care/procedures.
8. Instruct the subject returning to the site for the next follow up visit 6 weeks (42 ± 14 days) after the surgery date.

#### **9.1.4 Follow-up visits at 6 weeks (42 ± 14 days)**

1. Query subject regarding any changes in general health and the use of concomitant medications/therapies.
2. If any adverse device effects or device deficiencies are observed or reported, they must be recorded as instructed in Section 12 - Adverse Events and Device Deficiencies.

#### CONFIDENTIAL AND PROPRIETARY

This document contains information that is confidential and proprietary to Smith & Nephew PLC and Smith & Nephew, Inc. and is intended for use only by Smith+Nephew and its manufacturer. It shall not be reproduced or copied in whole or in part, nor shall the contents be disclosed by any means without prior written permission from Smith+Nephew, nor shall anyone make any use of it that is contrary to the expressed or implied wishes of Smith+Nephew.

Clinical Protocol	Study Number: CORI.2019.06
A Prospective, Multi-center, Randomized Controlled Study to Evaluate the Safety and Effectiveness of REAL INTELLIGENCE™ CORI™ in unicondylar knee arthroplasty (UKA) Procedure	Version: 4.0-Master, 07 Sep 2022 Page: 64 of 167

3. Verify with the subject if any revision has occurred since the last visit. If any revision is observed or reported, it must be recorded as instructed in Section 12 - Adverse Events and Device Deficiencies.
4. Collect the 2011 KSS score objective measures (joint alignment, instability, motions & symptoms).
5. Have the subject complete the 2011 KSS score subject questions.
6. Have the subject complete the OKS patient-reported outcome measure
7. Have the subject complete the EQ-5D-5L patient-reported outcome measure.
8. Have the subject complete the FJS-12 patient-reported outcome measure.
9. Collect the standing weight bearing long leg (A/P) and standard lateral (non-weight bearing) radiographic images of the affected knee. Review the images to complete the appropriate eCRF for leg alignment and component alignment.
10. Instruct the subject on follow-up procedures, including returning to the site for the next follow-up visit in 6 months ( $185 \pm 14$  days) after the surgery date.

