#### 4.4.5 Potential Adverse Effects

As with any surgical procedure, there is risk involved. Potential complications accompanying surgery may occur, including allergic reaction (anaphylactic and minor), infection, mild to serious physical injury, localized static shock, delay in the operation, surgical site nerve injury, vascular injuries of the lower extremity, soft tissue damage, major bone gouging at the surgical site, bone fracture, immature implant failure, unstable knee joint, limited or restricted knee range of motion, major blunt impact injury, unintended laceration/puncture wound, and osteonecrosis.

The CORI User's Manual (Document ID: 500230, REAL INTELLIGENCE™ CORI™ for Knee Arthroplasty) states the following warnings and cautions:

- CORI is a surgical tool designed to provide assistance to the surgeon; it is not a substitute for the surgeon's experience and skill. The surgeon is responsible for implant planning and the conduct of the surgery during which CORI is being used.

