### 8.2.2 Blinding

The study is non-blinded.

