### 8.3.1 Data Review and Quality Assurance

Data will be transcribed from the data source to an electronic Case Report Form (eCRF). All data requested on the eCRFs are considered required. Data points not collected and/or recorded will be considered deviations unless otherwise specified.

Data collection is the responsibility of the clinical trial staff at the site under the supervision of the Principal Investigator. The Principal Investigator is responsible for ensuring the accuracy, completeness, legibility, and timeliness of the data reported. The Principal Investigator must provide his/her electronic signature on the appropriate eCRFs to be documented in compliance with local regulations. Changes to data previously submitted to the sponsor will require a new signature by the Investigator to acknowledge/approve the changes.

Visual and computer data review will be performed in line with Smith and Nephew procedures to identify possible data discrepancies. Manual and automatic queries will be created within the electronic data capture system, and will be issued by Smith and Nephew to the site for appropriate response. Site staff are responsible for resolving all queries in the electronic data capture system.

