### 9.2.1 Leg alignment

The leg alignment should be measured from an antero-posterior (A/P) view standing weight bearing full leg ('long leg') x-ray. The following axes shall be identified:

- Mechanical Axis of the femur: Axis from the center of the femoral head to the center of the distal femur.
- Mechanical Axis of the tibia: Axis from the center of the proximal to the center of the distal tibia.

The angular deviation from the neutral position ( $180^\circ$ ) shall be measured as shown as "E" in Figure 9.2-9-1. The angular deviation from the neutral position shall be recorded in the eCRF.

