### Target Leg alignment (Surgical Plan)

The operative plan for leg alignment as entered in CORI shall be recorded in the eCRF for each subject. The planned leg alignment serves as the target for post-operative leg alignment. This may not be a neutral position.

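### The primary 6-week leg-alignment angle is read at site in a non-blinded trial, and nothing keeps the arm or the target from the reader

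*Protocol*

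**What the plan says.** The primary endpoint is the proportion of subjects whose 6-week leg alignment lies within 3 degrees of a subject-specific target (Protocol 8.4.1, 9.2.1, 10.4.1).

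- **Who reads.** Reading is a site visit step: staff are to "Review the images to complete the appropriate eCRF for leg alignment and component alignment" (9.1.4, step 9). Section 8.3.1 adds: "Data collection is the responsibility of the clinical trial staff at the site under the supervision of the Principal Investigator". The reader's role is not named.
- **Blinding.** "The study is non-blinded" (8.2.2). Section 8.5, on minimizing bias, covers multiple sites, randomized enrolment, attrition and pre-specified analysis. It does not mention outcome reading.
- **Target.** The operation visit includes "Collect data on the surgical plan: Target Leg alignment" (9.1.3, step 3). Section 9.2.1 says "The operative plan for leg alignment as entered in CORI shall be recorded in the eCRF for each subject" and "The planned leg alignment serves as the target for post-operative leg alignment". On planning, the user's-manual warnings in 4.4.5 state: "The surgeon is responsible for implant planning and the conduct of the surgery during which CORI is being used".
- **What is recorded from the film.** "The angular deviation from the neutral position shall be recorded in the eCRF" (9.2.1). The reader enters an angle from neutral, not a pass or fail against target.

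**The concern.** An operating surgeon cannot be blinded to robot or manual instruments. The person who measures the film can be, and the protocol does not ask for it. The endpoint is a cut-off on a continuous reading, so a small shift in a knee near 3 degrees turns a failure into a success. A reader who knows the target knows which way a helpful shift goes, and a reader who knows the arm could, without intending it, apply it to one arm only. Randomization, site balance and a pre-specified analysis do not correct this. The comparison is a superiority claim meant to support registration in mainland China (4.3), so an unprotected reading weakens the main evidence.

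**Working it through.** **1. The plan's own figure.** Section 11 gives 63 per group for 80% power, with 92.1% against 73.4%, and 70 after 10% attrition. For a two-sided 5% two-sample z-test with pooled variance, the mean rate is (0.921 + 0.734)/2 = 0.8275 and the difference is 0.187.

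n = [1.960 × √(2 × 0.8275 × 0.1725) + 0.842 × √(0.921 × 0.079 + 0.734 × 0.266)]² / 0.187² = 62.9, so 63. Then 63/0.9 = 70.

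The figure reproduces, and masking the reader would not change it.

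**2. Can the reader know arm and target?** Reading is done at the site (9.1.4, 8.3.1). The target is entered at the operation visit and kept in the eCRF (9.1.3, 9.2.1). The trial is open (8.2.2), and 8.5 sets no limit on who reads or what they see. The documents therefore permit a reader who knows both. They do not say that this is who reads.

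**3. Illustration of what a reading shift would do.** The documents give no reading error and no size of bias, so the following are assumptions:

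- Deviation from target is normal with mean 0.
- The SD is set so that 73.4% fall within 3 degrees: SD = 3 / z(0.867) = 3/1.1123 = 2.70. Section 11 takes 73.4% from total knees within 3 degrees of neutral, so using it for deviation from a personal target is itself an assumption.
- There is no true difference between arms, with 70 per arm.
- Every CORI film is read closer to its target by s degrees, and no conventional film is.

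Observed CORI rate = 2Φ((3 + s)/2.70) − 1. For s = 0.5 this is 2Φ(1.298) − 1 = 2 × 0.9028 − 1 = 80.6%.

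The decision rule is that of 10.4.1: superiority if the lower exact 95% limit for CORI exceeds the upper exact 95% limit for conventional. The false-superiority probability sums, over all pairs of counts 0 to 70, the binomial probabilities of the pairs that meet the rule.

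| Pull s (degrees) | Observed CORI rate | False gain (points) | False superiority, non-overlap rule |
|---|---|---|---|
| 0 | 73.4% | 0 | 0.16% |
| 0.25 | 77.2% | 3.8 | 0.7% |
| 0.5 | 80.6% | 7.2 | 2.5% |
| 1.0 | 86.2% | 12.8 | 14% |

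The false gain does not depend on the decision rule. At 0.5 degree it is 7.2 of the planned 18.7 points (92.1 − 73.4).

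**4. Sensitivity to the pattern of bias.** A 0.5-degree offset in one fixed direction, not toward target, lowers the rate slightly: Φ(2.5/2.70) − Φ(−3.5/2.70) = 72.6%. The same pull in both arms leaves the false-superiority rate at about 0.16%. The harm comes from shifts toward target that differ by arm, which is what knowing arm and target makes possible.

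**5. Is masking feasible?** The recorded value is the angle from neutral, so the target is not needed to read the film. Both arms receive the sponsor's implants (8.1). The principal investigator may delegate tasks within a qualified site team (22.6.1).

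**The case against.** The strongest reply has four parts.

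- **The protocol's rule is very conservative.** With no bias it gives false superiority of 0.16%, and with a 0.5-degree pull 2.5%, no more than the usual one-sided level. Only the 1-degree case goes clearly beyond it. This is correct for the error rate, but the estimated difference would still be inflated. A reader might apply a two-sample z-test, consistent with the sample size, and get about 17% and 48% at 0.5 and 1 degree. The protocol does not use that test to declare superiority, so those figures do not describe this plan.
- **The bias model is close to a worst case.** It pulls every CORI film toward its own target and touches no conventional film. That stands, and the figures are an illustration, not an estimate. Section 9.2.1 also defines both axes, which limits discretion.
- **Masking may leak or fail.** A reader might infer that hiding two fields from whoever now reads would remove most of the bias with no change in staff. The documents do not support this. They give no bias size and no masking effectiveness. An operating surgeon cannot be masked, and nothing shows that each of up to 8 sites has a qualified non-operating reader. CORI's bone screws and checkpoint pins (6.1.1) may leave traces on films. A discharge film may already have been seen. The surgeon scores alignment for the Knee Society Score at the same visit (9.2.4), which SAP 7.4 takes from a weight-bearing radiograph.
- **No comparison is left to bias.** The study ended on 15 May 2024 with four subjects (SAP 2). The data are listed only (SAP 7.1) and the primary analysis is marked not applicable (SAP 7.10). That limits the practical effect to the design and any reuse of it.

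**Conclusion.** The point holds as a design weakness: the primary angle is read at site in an open trial, and no provision keeps arm or target from the reader. A reader might go further and conclude that the operating surgeon does read the films. The documents neither say so nor exclude it.

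The possible size is a false gain of 7.2 to 12.8 points for a 0.5 to 1 degree pull. Under the non-overlap rule, false superiority rises from 0.16% to between 2.5% and 14%. These figures rest on the assumed normal deviation with SD 2.70 degrees, no true difference, 70 per arm and a pull confined to CORI films. The actual bias, and the share that masking would remove, cannot be computed from the documents. Because the trial stopped with four subjects and plans listings only, the conclusion concerns the design as written, not any result.

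**What to change.** In Protocol 9.1.4 (step 9) and 9.2.1, specify:

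1. The 6-week angle from neutral is measured on a film labelled with the subject number only.
2. The reader is a site team member who took no part in the operation, wherever the team already includes one.
3. The arm and target fields are hidden in the eCRF until the angle is saved.
4. The database, not the reader, calculates deviation from target and success.

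The cost is protocol wording, an eCRF setting and a minor change in who reads at some sites. No central reader is needed, and the sample size and endpoint stay as they are. Concealment will be imperfect, for example where pin traces show on the film, and at a site with no non-operating reader the arm cannot be hidden.

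This does not settle how the target is set in the conventional arm, because 9.2.1 defines it only as the plan entered in CORI. That needs its own clarification.

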#### **9.1.5 6 months ( $185 \pm 14$ days) after surgery**

1. Query subject regarding any changes in general health and the use of concomitant medications/therapies.
2. If any adverse device effects or device deficiencies are observed or reported, they must be recorded as instructed in Section 12 - Adverse Events and Device Deficiencies.
3. Verify with the subject if any revision has occurred since the last visit. If any revision is observed or reported, it must be recorded as instructed in Section 12 - Adverse Events and Device Deficiencies.

CONFIDENTIAL AND PROPRIETARY

This document contains information that is confidential and proprietary to Smith & Nephew PLC and Smith & Nephew, Inc. and is intended for use only by Smith+Nephew and its manufacturer. It shall not be reproduced or copied in whole or in part, nor shall the contents be disclosed by any means without prior written permission from Smith+Nephew, nor shall anyone make any use of it that is contrary to the expressed or implied wishes of Smith+Nephew.

Clinical Protocol	Study Number: CORI.2019.06
A Prospective, Multi-center, Randomized Controlled Study to Evaluate the Safety and Effectiveness of REAL INTELLIGENCE™ CORI™ in unicondylar knee arthroplasty (UKA) Procedure	Version: 4.0-Master, 07 Sep 2022
	Page: 65 of 167

4. Collect the 2011 KSS score objective measures (joint alignment, instability, motions & symptoms).
5. Have the subject complete the 2011 KSS score subject questions.
6. Have the subject complete the OKS patient-reported outcome measure
7. Have the subject complete the EQ-5D-5L patient-reported outcome measure.
8. Have the subject complete the FJS-12 patient-reported outcome measure.
9. Instruct the subject on follow-up procedures, including returning to the site for the next follow-up visit 12 months (365 ± 30 days) after the surgery date.

#### **9.1.6 Exit visit 12 months (365 ± 30 days) after surgery**

1. Query subject regarding any changes in general health and the use of concomitant medications/therapies.
2. If any adverse device effects or device deficiencies are observed or reported, they must be recorded as instructed in Section 12 - Adverse Events and Device Deficiencies.
3. Verify with the subject if any revision has occurred since the last visit. If any revision is observed or reported, it must be recorded as instructed in Section 12 - Adverse Events and Device Deficiencies.
4. Collect standard A/P and lateral radiographic images of the affected knee. Review the images to complete the appropriate eCRF for standard radiographic evaluation (presence of radiolucent lines, osteolysis and implant migration).
5. In case a standing long leg X-ray is taken as a standard of care, please complete the respective leg alignment eCRF (optional).

#### CONFIDENTIAL AND PROPRIETARY

This document contains information that is confidential and proprietary to Smith & Nephew PLC and Smith & Nephew, Inc. and is intended for use only by Smith+Nephew and its manufacturer. It shall not be reproduced or copied in whole or in part, nor shall the contents be disclosed by any means without prior written permission from Smith+Nephew, nor shall anyone make any use of it that is contrary to the expressed or implied wishes of Smith+Nephew.

Clinical Protocol	Study Number: CORI.2019.06
A Prospective, Multi-center, Randomized Controlled Study to Evaluate the Safety and Effectiveness of REAL INTELLIGENCE™ CORI™ in unicondylar knee arthroplasty (UKA) Procedure	Version: 4.0-Master, 07 Sep 2022
	Page: 66 of 167

6. Collect the 2011 KSS score objective measures (joint alignment, instability, motions & symptoms).
7. Have the subject complete the 2011 KSS score subject questions.
8. Have the subject complete the OKS patient-reported outcome measure
9. Have the subject complete the EQ-5D-5L patient-reported outcome measure.
10. Have the subject complete the FJS-12 patient-reported outcome measure.
11. Complete Exit Visit eCRF.

